At the time this protocol amendment is issued, a total of 3,054 PE patients were enrolled including 121 PE positive patients (uncleaned, non-final data). Thus, the PE data collection has been completed and data cleaning is in progress.

Expected overall study enrolment - DVT

Enrolment is still ongoing for DVT patients, for which the following estimated enrolments were calculated:

DVT estimated enrolment:

Based on actual prevalence data, a total of 1,870 subjects are expected to participate in the DVT study—with at least 1,032 from the US and at most 568 from OUS—to have 90% power to demonstrate STA® - Liatest® D-Di XL efficacy for DVT.

In summary, the two trials are expected to enroll a total of 4,924 subjects.

Note: some patients might have both PE and DVT indications and, therefore, contribute to both enrolment counts, hence the “at most” mention.

It is important to note that the above sample size is based on specific prevalence assumptions for DVT in the US and OUS. Blind sample size re-estimation has been specified for the DVT study separately to re-calculate sample size during the trial based on prevalence of reference-positive cases. Counting reference-positive will be done blind to STA® - Liatest® D-Di XL outcome.

Total expected duration of the study: around 48 months (from beginning of enrolment to site closure)

Total duration by subject: maximum duration of 4 months

Follow-up: All patients with low or moderate Wells score for whom VTE is excluded as per site standard of care (SOC) will be followed for 3 months to evaluate potential development of DVT and/or PE.

Statistical Considerations

Sample Size Justification: Presentation of the sample sizes noted in the synopsis above is based on meeting performance goals using two-sided, exact binomial 95% confidence intervals based on the following assumptions:

- US prevalence of reference-positive = 3.4% and 5.3% for PE and DVT respectively
- OUS prevalence of reference-positive = 5.7% and 8.1% for PE and DVT respectively
- D-Di XL sensitivity = 98% for both PE and DVT
- D-Di XL NPV = 99.6% for both PE and DVT

Statistical Hypotheses for Co-primary Endpoints: The following co-primary hypotheses are specified separately for PE and DVT:

H_0 : NPV ≤ 0.95

H_1 : NPV > 0.95

and

H_0 : Sensitivity ≤ 0.90

H_1 : Sensitivity > 0.90

Additionally, we will need to show that point estimates for NPV and are sensitivity ≥ 0.97 and ≥ 0.95 respectively in both indications.

TABLE OF CONTENTS

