Ensuring Requisite Power: The co-primary hypotheses in this trial relate to NPV and Sensitivity. To obtain requisite power for both co-primary endpoints a minimal number of VTE positive cases (for testing sensitivity) and D-Di negative cases (for testing NPV) is needed. Our computations indicate that having a sufficient number of VTE positive cases for testing sensitivity will, due to low VTE positive prevalence, yield a sufficient number of D-Di negative cases as well; when power for sensitivity is near the desired 90%, power for NPV is near 100%. Thus, determination of sample size is driven by the trial's requirement for sensitivity.

The trial will conclude after enough VTE positive cases have been recruited to achieve requisite power.

As noted in Section 4.2 blood samples will be tested for stability using the VIDAS D-dimer assay and only those determined stable will be included in this study (and tested with STA® - Liatest® D-Di XL). It is important to note that:

- a. VIDAS® D-Dimer Exclusion II assay was chosen because its precision is highest of all FDA approved assays in the indication. Greater precision is expected to yield a better assessment of stability since measurement error (random variation in outcome) may cause sample to be wrongly classified as “unstable”.
- b. A blood sample that has been frozen and thawed, and shown stable by testing (within acceptable error) is equivalent to the fresh sample. Consequently, testing stable frozen/thawed samples with STA® - Liatest® D-Di XL is equivalent to having tested the sample fresh.

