9.5 SAMPLE SIZE CONSIDERATIONS

Presentation of sample size in this study is based on demonstrating STA® - Liatest® D-Di XL effectiveness in "unlikely" subjects for VTE meets the following performance goals as provided in Table 1A of CLSI guideline (H-59A p. 28):

- Sensitivity

³ U.S. Dept. of HHS, FDA. Guidance for industry: E9 statistical principles in clinical trials. 1998; Section 5.2.1, pp. 28 –

- Lower 95% two-sided confidence interval (LCL) ≥ 0.90
- Point Estimate ≥ 0.95
- NPV
 - LCL 95% two-sided ≥ 0.95
 - Point Estimate ≥ 0.97

While performance goals (PGs) are the same for PE and DVT, power must be calculated separately for each because of different prevalence and accuracy assumptions for PE+ and DVT+. The accuracy assumptions are based on observed results in the studies submitted to FDA⁴. Notwithstanding, blind sample size re-estimation (i.e. counting of positive cases during the trial) will be employed to achieve requisite power. For both PE and DVT sample sizes we assume that at about 70% of reference-positive cases will be from the US and the rest (about 30%) from out of US (OUS).

PE: Power for Meeting PGs

Presentation of sample size is based on obtaining a enough reference-positive cases to achieve 90% power to meet the LCL PG for sensitivity (≥ 0.90), which will necessarily:

- Enable success on the point estimate PG for sensitivity, since the minimum true-positive rate needs to meet the LCL PG, given the sample size reported below, is the same as the minimum needed for the point estimate PG.
- Yield enough reference-negative patients for near 100% power to meet the PGs for NPV, due to low prevalence of positive cases.

Based on the counting of positive cases (allowed by this protocol) to the date of amendment V2.1, we assume:

- US prevalence of reference-positive = 3.4%
- OUS prevalence of reference-positive = 5.7%

Based on historical data, we assume:

- D-Di XL sensitivity = 98%
- D-Di XL NPV = 99.6%

Given the above, N = 115 reference-positive subjects are needed to have at least 90% power to demonstrate efficacy on both sensitivity and NPV⁵. Given at least N = 75 in the US (65%), 2,206 “unlikely” US subjects will be needed (75/0.034). Given N = 40 OUS (35%) at most1, 702 “unlikely” OUS subjects will be needed (40/0.057).

⁴ In these studies, DVT results demonstrate higher accuracy parameters than PE. For the purpose of computing power in this study we assume the PE accuracy observed for both indications.

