⁵ Achieving requisite power for sensitivity, rather than NPV, drives the sample size

At the time this protocol amendment is issued, a total of 3,054 PE patients were enrolled including 121 PE positive patients (79 in US and 42 OUS - uncleaned, non-final data), allowing to have 90% power to demonstrate D-Di XL efficacy for PE. The PE data collection has been completed and data cleaning is in progress.

DVT: Power for Meeting PGs

Presentation of sample size is based on obtaining enough reference-positive case to achieve 90% power to meet the confidence interval PG for sensitivity (≥ 0.90), which will necessarily provide:

- The same power to meet the point estimate PG, since the minimum true-positives needed to meet the confidence interval PG is the same as that needed to meet the point estimate PG.
- A sufficient number of reference-negative patients for near 100% power to meet the PGs for NPV, due to low prevalence of positive cases

Based on data previously submitted to FDA, we assume:

- US prevalence of reference-positive = 5.3%
- OUS prevalence of reference-positive = 8.1%
- D-Di XL sensitivity = 98%
- D-Di XL NPV = 99.6%

Given the above, $N = 115$ reference-positive subjects are needed to have 90% power to demonstrate efficacy. Given at least $N = 69$ in the US (60%), at least 1,032 “unlikely” US subjects will be needed ($69/0.053$). Given $N = 46$ OUS (40%) 568 “unlikely” OUS subjects will be needed ($46/0.081$).

In summary, a total of 1,870 subjects are expected to participate in the DVT part of the study—at least 1,032 from the US and at most 568 from OUS—to have 90% power to demonstrate D-Di XL efficacy for DVT.

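### The US DVT enrolment floor is printed as 1,032 in three places, but the plan's own formula (69/0.053) and its stated totals give 1,302

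*Combined protocol and SAP*

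**What the plan says.** Section 9.5, under the DVT power heading, sets a target of 115 cases: "reference-positive subjects are needed to have 90% power to demonstrate efficacy". It splits them into 69 from the US (60%) and 46 from outside the US (OUS, 40%). Each count is divided by an assumed prevalence, 5.3% in the US and 8.1% OUS. The US quotient, 69/0.053, is printed beside the result 1,032, and the OUS quotient, 46/0.081, beside 568.

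The closing summary of Section 9.5 states that "a total of 1,870 subjects are expected to participate in the DVT part of the study", made up of "at least 1,032 from the US and at most 568 from OUS". The Protocol Summary repeats the regional figures ("with at least 1,032 from the US and at most 568 from OUS") and the total of 1,870, and adds that "the two trials are expected to enroll a total of 4,924 subjects". The same part of the Protocol Summary reports 3,054 PE patients already enrolled.

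Two statements limit how far the enrolment number governs the trial. Section 9.2 says "The trial will conclude after enough VTE positive cases have been recruited to achieve requisite power". Section 9.5 says of blinded sample size re-estimation: "counting of positive cases during the trial) will be employed to achieve requisite power".

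Section 9.5 also says, for both indications, "we assume that at about 70% of reference-positive cases will be from the US".

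**The concern.** The figure 1,032 does not follow from the formula printed next to it, and it does not fit the total in the same sentence. DVT is the indication still enrolling, and this is the amendment for US sites, so the wrong number is the US enrolment figure for the open cohort. It is presented as the number of US subjects that delivers 69 US positives. A site, ethics committee or regulator who used it for planning would expect 270 fewer US subjects than the plan's own assumptions require, and the target of 115 positives would probably be missed.

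**Working it through.** **Inputs.** From Section 9.5 (DVT): 115 reference-positives, 69 US and 46 OUS; prevalence 5.3% US and 8.1% OUS; sensitivity 98%. From Sections 9.5 and 9.6: success on sensitivity requires an exact two-sided 95% lower limit of at least 0.90 and a point estimate of at least 0.95. From the Protocol Summary: 3,054 PE patients enrolled, DVT total 1,870, combined total 4,924.

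**Step 1: the plan's method, subjects = positives / prevalence.**
- DVT, OUS: 46/0.081 = 567.9, so 568. Reproduces.
- PE, US: 75/0.034 = 2,205.9, so 2,206. Reproduces.
- PE, OUS: 40/0.057 = 701.8, so 702. Reproduces, and 2,206 + 702 = 2,908 as stated.
- DVT, US: 69/0.053 = 1,301.9, so **1,302**. The printed 1,032 does not reproduce; the gap is 1,302 − 1,032 = 270, or 21% of 1,302.

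**Step 2: the totals.**
- 1,302 + 568 = 1,870, as stated; 1,032 + 568 = 1,600.
- 3,054 + 1,870 = 4,924, as stated; 3,054 + 1,600 = 4,654.
- With a total of 1,870 and at most 568 OUS, the US minimum is 1,870 − 568 = 1,302. Stopping the US at 1,032 would need 1,870 − 1,032 = 838 OUS subjects, above the stated cap of 568.

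**Step 3: can another stated input give 1,032?** A 70% US share gives 0.70 × 115/0.053 = 1,519. Solving backwards, 69/1,032 implies a prevalence of 6.7%, which appears nowhere. No dropout allowance is stated for this calculation. None of these explains 1,032.

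**Step 4: expected positives.**
- US at 1,032: 1,032 × 0.053 = 54.7. US at 1,302: 1,302 × 0.053 = 69.0.
- OUS: 568 × 0.081 = 46.0.
- Total: 100.7 with 1,032 and 115.0 with 1,302.

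**Step 5: a hypothetical stop at the printed regional figures.** This would require ignoring both the total of 1,870 and the counting of positives. The number of positives is modelled as the sum of two independent binomials, Bin(US, 0.053) + Bin(568, 0.081), with every subject treated as evaluable. Power is averaged over that distribution at a true sensitivity of 98%.

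| | 1,032 US + 568 OUS | 1,302 US + 568 OUS |
|---|---|---|
| Expected positives | 100.7 | 115.0 |
| Chance of at least 115 positives | 8.0% | 51.4% |
| Chance of fewer than 100 positives | 45.6% | 6.5% |
| Average exact power, sensitivity | 91.1% | 95.0% |

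At fixed counts, 115 positives need at least 110 true positives (lower limit 0.9015) and power is 97.1%. With 101 positives, at least 97 are needed (lower limit 0.9017) and power is 94.7%.

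**Step 6: the split between regions.** The derivations use 75/115 = 65% US for PE and 69/115 = 60% US for DVT. Section 9.5 states about 70% for both.

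**The case against.** The strongest reply is that this is a slip with no effect on inference. The sentence gives a floor and a cap, not two numbers to be added, and 1,302 US plus 568 OUS meets both, so strictly a floor of 1,032 is uninformative rather than in conflict with the total. The 1,870 already contains the right US number, the trial ends on the count of positives, and no test, performance goal, analysis set or stopping rule uses 1,032. The probabilities in Step 5 describe a course that the plan excludes.

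Most of this stands, and it limits the consequence. It does not make 1,032 correct: the figure still contradicts its own printed formula, and the total and cap together imply a floor of 1,302.

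Three further reservations are fair:
- The yields treat every enrolled subject as evaluable. The Protocol Summary asks for 115 evaluable positives, and unstable samples, failed quality control, missing reference results and major deviations are all excluded, so real yields would be lower under either figure.
- The 4,924 is a sum of two enrolment counts. The Protocol Summary notes that patients with both indications count in each, so it need not be a number of distinct people. Only the addition is confirmed here.
- The PE text has its own wording mismatch: the OUS figure of 702 is a minimum in the Protocol Summary, while Section 9.5 attaches a maximum to the OUS PE number. That is separate from the DVT figure.

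**Conclusion.** The US DVT floor is wrong as written in all three places. By the plan's own formula and totals it should read 1,302, a difference of 270 subjects. This conclusion rests only on arithmetic from stated inputs.

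The 90% power statement is not broken. Even the hypothetical stop at 1,032 and 568 leaves average power for sensitivity at 91.1%, given 98% sensitivity, the stated prevalences and full evaluability. What would be missed in that case is the plan's target of 115 positives, by about 14 on average (115.0 − 100.7 = 14.3).

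The mismatch between a 70% US share and the 65% and 60% actually used is real but secondary, and it does not explain 1,032. The figure should be corrected because it concerns the indication still enrolling and the correction is nearly free.

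**What to change.** Replace 1,032 with 1,302 in the Section 9.5 DVT derivation, in the Section 9.5 DVT summary sentence and in the Protocol Summary. Leave 1,870 and 4,924 as they are. In the same edit, replace the general 70%/30% sentence in Section 9.5 with the splits used: 65/35 for PE and 60/40 for DVT.

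The cost is one figure in three places and one sentence, in the next amendment. The target of 115 positives, the hypotheses, the performance goals and the rule for ending enrolment do not change, and no additional patients are required.

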9.6 STATISTICAL ANALYSIS

Overview

The data will be summarized in tables listing the mean, standard deviation, median, minimum, maximum and number of subjects for continuous data or in tables listing count and percentage for categorical data, where appropriate. Data listing by subject will be provided.

The effects of noncompliance, dropouts, and possible covariates, will be assessed to determine the impact on the general applicability of results from this study.

All statistical analyses will be performed and data appendices will be created using the SAS® system.

Subject Disposition

Subject disposition will be tabulated; the number of enrolled, exposed, prematurely terminated and completed subjects will be summarized overall and by Device status.

A list of dropouts will be prepared including reason for discontinuation, and time of discontinuation.

Primary Analysis

Primary analysis will be conducted using Primary efficacy analysis set and will be done separately for PE and DVT.

Co-primary Analysis I

NPV will be computed in the usual manner as follows:

$$NPV = TN / (TN + FN)$$

Where,

TN = No. of true negative subjects

FN = No. of false negative subjects

We will test NPV using the following hypotheses:

$$H_0: NPV \leq 0.95$$

$$H_1: NPV > 0.95$$

An exact binomial confidence interval will be used, where success will be declared if the two-sided 95% LCL is at or above the PG specified.

Additionally, we require: Point estimate of $NPV \geq 0.97$.

Co-primary Analysis II

Sensitivity will be computed in the usual manner as:

$$Sensitivity = TP / (TP + FN)$$

Where,

TP = No. of true positive subjects

FN = No. of false negative subjects

We will test Sensitivity using the following hypotheses:

H_0 : Sensitivity ≤ 0.90

H_1 : Sensitivity > 0.90

An exact binomial confidence interval will be used, where success will be declared if the two-sided 95% LCL is at or above the PG specified.

Additionally, we require: Point estimate of Sensitivity ≥ 0.95 .

Success for DVT will be declared if the four DVT PGs have been met.

Success for PE will be declared if the four PE PGs have been met.

Covariate Analyses, Including Poolability

The effect of the following covariates will be examined on Device accuracy:

- Age (measured continuously),
- Gender,
- Sites within US and OUS separately (enrolling sites with at least 20 subjects will be included separately. Sites with a smaller number of subjects will be combined into a single, "other" site). This is a test of site poolability within US and OUS separately.
- Region (US, OUS), which is a test of poolability of the US and OUS populations,
- PTP (measured by validated and standardized test).

Effect of covariates will be assessed for each covariate individually using the following logistic regression model:

Device = Cov + Reference Standard + Cov*Reference Standard

Where,

Device – D-dimer XL result (dichotomous)

Reference Standard – Diagnosis by imaging or follow-up (dichotomous)

Cov – Relevant covariate (categorical or continuous, depending on covariate)

Additional potential covariates will be compared between US and OUS and, if found significant, will be analyzed using the model described above.

In this model we are interested in the Cov*Reference interaction, whereby a significant result indicates that Device performance relative to Reference Standard is affected by the covariate.

Secondary Analysis

The following will be provided for Primary analysis sets:

- Specificity,
- Positive Predictive Value,
- Positive and negative likelihood ratios.
- Prevalence of reference positive cases

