- 1) The initial phase (see diagram below) will include sample and data collection from subjects suspected of VTE (PE and/or DVT) at participating sites (“enrolling sites”); subjects will be diagnosed and treated in accordance with routine standard of care (SOC). A test using VIDAS® D-Dimer Exclusion II™ (VIDAS) assay will be conducted on one of the frozen plasma aliquots. The result obtained (i.e. D-Di “reference value”) will be used in the following phase to assess sample stability.

- 2) When the STA® - Liatest® D-Di XL product is ready for clinical testing (see diagram below), frozen samples from unlikely patients will be tested with VIDAS assay and with STA® - Liatest® D-Di XL. The results of the VIDAS assay will be used to assess samples stability. The results from “stable” samples will be used for comparison to reference (imaging or follow-up) and computation of accuracy parameters (sensitivity, NPV, specificity and PPV). STA® - Liatest® D-Di XL and stability testing will be performed at selected sites (“testing sites”). There will be at least 2 testing sites in the US and 2 in Europe.

Procedures for STA - Liatest DDi XL clinical testing

Main inclusion criteria: The study population will be recruited from prospective, consecutive, ambulatory outpatients (presenting at the emergency unit or outpatient clinic) suspected of having VTE. Patients with DVT and PE will be analyzed as separate groups. Therefore, enrolment in each group will be monitored separately and will be stopped when the desired target per indication is reached. Subjects suspected of both DVT and PE will be included in both PE and DVT groups.

Number of Subjects

A sample size of $N = 115$ evaluable reference-positive subjects is needed to achieve at least 90% power to demonstrate sensitivity for PE and DVT separately. This will provide at least 80% power to demonstrate co-primary performance goals for PE and co-primary performance goals for DVT. The samples needed to obtain the number of positives will, due to low prevalence, yield a large number of negative subjects so that power for demonstrating NPV performance goals is about 100% in each indication.

Expected overall study enrolment – PE

Based on actual prevalence data obtained during enrolment, a total of at least 2,908 subjects were expected to participate in the PE study—with at least 2,206 from the US and at least 702 from OUS—to have 90% power to demonstrate STA® - Liatest® DDi XL efficacy for PE.

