6.4.1. Instruments

STA® - Liatest® D-Di XL test will be performed at testing sites (see sec. 2.1) on frozen banked samples using Stago instruments from Max® generation of the following families: STA-R® family , STA Compact® family or STA –Satellite® family (currently under development – will be included if available at the time testing with STA® - Liatest® D-Di XL begins).

The use of these instruments with STA® - Liatest® D-Di XL will require updated software version including :

- Modification in the homogenization process of reactional medium containing D-dimer plasma and anti-D-dimer antibodies
- Modification of the signal processing and calibration curve.

Software changes will be implemented only for the STA® - Liatest® D-Di XL test and they will not impact the instrument configuration used for other D-Dimer assays.

If one of the above mentioned Stago analyzer is already routinely used at the testing site, at the beginning of the testing phase a full check of the instruments, including application of the new

²Wells PS. Integrated strategies for the diagnosis of venous thromboembolism. *J Thromb Haemost*. 2007;5(Suppl. 1):41-50

Country-specific amendment for US sites

software version mentioned above, will be performed by Stago personnel. In addition, the performance of the instruments will be verified during site visits performed by Stago Technical personnel before study starts and will appear in the relevant validation report. The necessary quality control of the instruments should be performed by the laboratory personnel as per routine practice described in the instructions for use. This will be verified by the assigned monitor during monitoring visit.

The serial numbers and software versions will be recorded at the start of the study and included in the validation report.

If none of the above mentioned Stago analyzers are routinely used at the testing site, then at the beginning of the study Stago personnel will implement the Stago analyzer(s) at the site strictly following the process used by Stago to implement the analyzer in routine practice at clinical sites.

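### Poolability is tested by enrolling site and region, with no testing-site or analyser factor, and only through the interaction, so a shift at the cut-off can go unflagged

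*Combined protocol and SAP*

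**What the plan says.** **Poolability (protocol 9.6, Covariate Analyses).** The named covariates are age, gender, enrolling site, region and pre-test probability. Site enters as "Sites within US and OUS separately (enrolling sites with at least 20 subjects will be included separately", with smaller sites merged. Region is listed as "Region (US, OUS), which is a test of poolability of the US and OUS populations". Each covariate is fitted alone in the logistic model "Device = Cov + Reference Standard + Cov*Reference Standard", and the plan then states: "In this model we are interested in the Cov*Reference interaction". A catch-all follows: "Additional potential covariates will be compared between US and OUS and, if found significant, will be analyzed using the model described above".

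**Where the result is generated.** The protocol summary says "There will be at least 2 testing sites in the US and 2 in Europe". Under 4.3 a testing site may also enrol patients, but need not. Section 6.4.1 has the assay run "using Stago instruments from Max® generation of the following families", listed as "STA-R® family , STA Compact® family or STA –Satellite® family", the last only if it is available in time. The analysers need updated software that changes homogenisation, signal processing and the calibration curve. Under 6.4.5 each sample is run once and called positive at or above 0.50 µg FEU/ml.

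**Other controls.** Instruments are checked technically before use, and serial numbers and software versions go into a validation report (6.4.1). Quality controls run at least daily (6.4.5). A result counts as valid only if its controls are in range (9.4).

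**Timing.** The PE and DVT SAPs are to be signed before data lock for whichever indication finishes first (9.1).

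**The concern.** There are two gaps, and they compound.

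1. **Which factor is tested.** Enrolling site describes where the patient came from. A difference in how the assay performs would arise where it is run, at the testing site and on a given analyser. Neither is named. The catch-all admits a further factor only if it differs significantly between US and OUS, so two testing sites in the same region could disagree without either being examined.

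2. **Which term is read.** With the device result as the outcome, Cov*Reference tests whether the diagnostic odds ratio differs between levels of the covariate. That is not the same as testing whether sensitivity differs. If one analyser reads low near the cut-off, fewer diseased and fewer non-diseased patients test positive: sensitivity falls, specificity rises, and the odds ratio can stay constant. The change then sits in the Cov main effect. A significant interaction is fair evidence that performance varies, but a non-significant one does not show that sensitivity is the same everywhere.

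At stake is the support for pooling. Following the stated rule, the report could conclude that results are poolable while one testing site or analyser has materially lower sensitivity than the rest.

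**Working it through.** **Step 1. The plan's own figure.** Inputs from 9.5: 115 reference-positives, sensitivity 0.98, exact two-sided 95% lower limit at least 0.90, point estimate at least 0.95.
- 110/115 true positives gives a lower limit of 0.9015; 109/115 gives 0.8899. So at most 5 false negatives are allowed. 110 is also the minimum for the 0.95 point estimate, as 9.5 says.
- P(FN ≤ 5 | n = 115, p = 0.02) = 0.971. The stated power of at least 90% holds as a floor.
- The plan gives no power for the poolability test.

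**Step 2. Baseline specificity.** None is stated. Sensitivity 0.98 and NPV 0.996 imply FN = 0.02 × 115 = 2.3 and TN = 2.3 × 0.996/0.004 = 572.7.
- PE: 572.7/(2,908 − 115) = 0.205.
- DVT: 572.7/(1,870 − 115) = 0.33.

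The range used is 0.205 to 0.60.

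**Step 3. A pure cut-off shift.** Subtract the same amount d from logit(sensitivity) and logit(1 − specificity). The interaction is then exactly zero by construction.
- Sensitivity 0.98 to 0.94: d = 3.892 − 2.752 = 1.140.
- Sensitivity 0.98 to 0.90: d = 3.892 − 2.197 = 1.695.
- Example: at specificity 0.60, logit(0.40) = −0.405. Subtracting 1.140 gives −1.545, so 1 − specificity = 0.176 and specificity = 0.824.

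**Step 4. How often each term flags it.** Simulation of the 9.6 model, 2,000 trials per scenario, DVT total 1,870, one quarter of samples shifted, likelihood-ratio tests at 5%.

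| Baseline specificity | Shifted sensitivity / specificity | Interaction flags | Main effect flags | All four goals met | Goals met, no interaction flag |
|---|---|---|---|---|---|
| 0.205 | 0.94 / 0.446 | 7.5% | 100% | 87.1% | 80.1% |
| 0.205 | 0.90 / 0.584 | 6.7% | 100% | 68.4% | 63.6% |
| 0.40 | 0.94 / 0.676 | 8.6% | 100% | 87.1% | 79.4% |
| 0.40 | 0.90 / 0.784 | 7.5% | 100% | 67.5% | 62.3% |
| 0.60 | 0.94 / 0.824 | 8.2% | 100% | 86.0% | 78.3% |
| 0.60 | 0.90 / 0.891 | 7.6% | 100% | 69.6% | 64.0% |

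For comparison, with no shift the interaction flags about 3% and the main effect about 5%. For PE (2,908 subjects) the interaction rates also lie within about 7–10%.

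The result is not an artefact of the logit scale. With a probit shift in the same six DVT scenarios, the interaction flags 6.7–11.8%. Over PE and DVT, shares of one quarter to one half, specificity 0.205–0.75, sensitivity falling to as low as 0.85 and either scale, the range is 2.5–13.6%. A Wald test flags at most 3.4%.

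**Step 5. Loss of sensitivity alone, specificity unchanged.** The pattern reverses.
- One quarter of samples at sensitivity 0.90: interaction about 45%, main effect about 4%.
- Half of samples: interaction 26–28% at sensitivity 0.94 and 51–52% at 0.90; main effect about 5%.

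Neither term is sufficient by itself.

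**Step 6. What a per-site table can show.** If 115 positives were spread evenly over four sites, each would have about 29. With 29/29 detected, the exact lower limit is 0.025^(1/29) = 0.881, below 0.90.

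**The case against.** **Region and the catch-all.** A reader might infer that enrolling site is the only poolability test. That is not so: region is named as one, and the catch-all could bring in testing site or analyser. This stands. Neither closes the gap, because the catch-all is conditional on a US–OUS difference and both routes rely on the same interaction.

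**Analyser families.** A reader might infer that the study supports a claim for every family. The documents make no such claim; the families are joined by an or, and the third is conditional. The analyser part therefore applies only if more than one family is used. The testing-site part does not depend on this.

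**Existing controls.** Instrument verification, daily quality control and the in-range rule do reduce the risk. None of them compares patient results between testing sites or analysers.

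**Interpreting the interaction is defensible.** A main effect can arise from case mix, and with thousands of samples a small difference will be significant. This stands and limits how the main effect should be used. It does not justify ignoring it.

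**The pooled goals.** A reader might infer that a pass with one weak site would be a false success. The documents do not support that: with 29 of 115 positives at sensitivity 0.90 and 86 at 0.98, true pooled sensitivity is (86 × 0.98 + 29 × 0.90)/115 = 0.960, above both goals. The stated hypotheses concern the pooled value.

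**Storage time.** A reader might want it added as a further covariate. Sections 4.2 and 6.5 already screen samples by paired VIDAS testing, and nothing here argues for more.

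**Conclusion.** The point holds as an improvement to the covariate analysis. Section 9.6 prespecifies no factor for the place or analyser where the device result is generated, and it reads a term that is nearly blind to a cut-off shift: about 7–10% detection against about 100% for the main effect, with one quarter of samples affected and sensitivity falling from 0.98 to 0.94 or 0.90. Because a loss of sensitivity alone shows mainly in the interaction, the main effect must be read in addition to it, not in its place.

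These rates rest on assumptions outside the documents: the share of samples affected, the size of the shift, baseline specificity of 0.205 to 0.60, a 5% test level and an equal shift on the logit scale. The documents do not say how samples are allocated to testing sites. The finding shows what the stated rule could miss; it is not evidence that any analyser is shifted, and it leaves the primary analysis and success criteria unchanged.

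**What to change.** Before the PE and DVT SAPs are signed:

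1. Add testing site and, if more than one is used, analyser family to the covariate list in 9.6.
2. Record both against each D-Di XL result. Section 6.4.1 collects serial numbers for the validation report but does not say that each result is linked to an instrument.
3. For these factors, examine the Cov main effect as well as Cov*Reference, and state how the main effect is tested (for example, by a likelihood-ratio test in the model without the interaction).
4. Tabulate sensitivity, specificity and NPV with exact 95% confidence intervals by testing site and analyser family, labelled descriptive.
5. State that a main effect triggers review and is not a pass/fail rule. The VIDAS result from the same thaw (4.2, 6.4.5) offers a comparator for separating an assay difference from case mix.

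The cost is a few models and tables and one linkage check, with no extra patients. The limits should be stated too: per-site sensitivity is too imprecise to confirm the 0.90 goal, and some main effects will turn out to be case mix.
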